2. SUMMARY OF KEY PROTOCOL INFORMATION

2.1. Changes to the Protocol Defined Statistical Analysis Plan

There were no changes or deviations to the originally planned statistical analysis specified in the protocol (Dated: 26/AUG/2019 Version: 208132/03).

2.2. Study Objective(s) and Endpoint(s)

Objectives	Endpoints
Primary Objectives	Primary Endpoints

 To evaluate the antiviral activity of GSK3640254 in HIV-1 infected Treatment-Naïve(TN) participants during 10 days of monotherapy in Part 1 and during 7 days of monotherapy in Part 2 	
 Maximum change from baseline (Day 1) in plasma HIV-1 ribonucleic acid (RNA)
Secondary Objectives	Secondary Endpoints

 To assess the safety and tolerability of GSK3640254 when administered as monotherapy over 10 days in Part 1 and over 7 days in Part 2 in HIV-1 infected TN participants 	
 GSK3640254 safety and tolerability parameters: adverse events (AE) ; post-baseline values and changes over time of clinical laboratory evaluations, vital signs, and electrocardiogram (ECG) parameters

 To characterize the pharmacokinetics of GSK3640254 dosing for 10 days in Part 1 and for 7 days in Part 2 in HIV-1 infected patients 	
 GSK3640254 PK parameters at the following dose administration: Day 1: area under the plasma concentration time curve from zero to 24 (AUC[0-24]), maximum observed concentration (C_{max}), time to maximum observed concentration (t_{max}), concentration at 24 hours post dose (C₂₄), absorption lag time (t_{lag}). Following repeat administration: Area under the curve (Area under the plasma drug concentration-time curve from pre-dose to the end of the dosing interval at steady state (AUC[0-τ]), C_{max}, t_{max}, pre-dose concentration (C₀), concentration at end of dosing interval (C_τ), apparent terminal phase half-life (t_{1/2}), and apparent oral clearance (CL/F), if data permit.

 To explore the relationship between GSK3640254 exposure and change in plasma HIV-1 RNA 	
 GSK3640254 repeat-dose PK parameters AUC(0-τ), C_{max}, C_τ with maximum HIV-1 RNA change from baseline

 To estimate GSK3640254 accumulation following administration of GSK3640254 for 10 days in Part 1 and for 7 days in Part 2 in HIV-1 infected patients 	
 Accumulation: GSK3640254 PK accumulation ratios (R): repeat -dose AUC (0-τ), C_{max}, and C_τ compared to Day 1 AUC (0-24), C_{max}, C₂₄, respectively

CONFIDENTIAL

208132

Objectives	Endpoints

 To examine dose proportionality of GSK3640254 PK parameters following dosing for 10 days in Part 1 and for 7 days in Part 2 	
 Relationship between Day 1 AUC (0-24), C_{max}, C₂₄, and repeat-dose AUC (0-τ), C_{max} and C_{τ} and GSK3640254 dose levels
Exploratory Objectives	Exploratory Endpoints

 To assess the development of viral resistance (genotypic and phenotypic) over 10 days in Part 1 and over 7 days in Part 2 and correlate with viral response, if appropriate. 	
 Emergence of drug resistance mutations, if appropriate

 To assess attainment of steady state following administration of GSK3640254 for 10 days in Part 1 and for 7 days in Part 2 in HIV-1 infected patients. 	
 Steady State: pre-morning dose concentrations (C₀) on Day 2 through Day 10 C_{τ} (Day 11) in Part 1 and on Day 2 through Day 7 C_{τ} (Day 8)

 To assess the immunologic effects of GSK3640254 when administered over 10 days in Part 1 and 7 days in Part 2 in HIV-1 infected adults 	
 Change from baseline in CD4+ T-cell count to Day 11 in Part 1 and to Day 8 in Part 2

 To explore the relationship between GSK3640254 exposure and safety or immunologic parameters, if appropriate 	
 GSK3640254 repeat-dose PK parameters: AUC (0-τ), C_{max}, C_{τ} with Day 11 change from baseline in CD4+ cell count in Part 1 and with Day 8 change from baseline in CD4+ cell count in Part 2

2.3. Study Design

Overview of Study Design and Key Features	

The diagram illustrates the study design, divided into Part 1 and Part 2. Part 1 starts with N=14 participants randomized on Day 1. They are assigned to three groups: GSK3640254 200 mg once daily (N=6), GSK3640254 10 mg once daily (N=6), and PLACEBO (N=2). Part 2 starts with N=20 participants randomized on Day 1. They are assigned to four groups: GSK3640254 Dose 90% Max Effect 140 mg (N=6), GSK3640254 Dose 75% Max Effect 80 mg (N=6), GSK3640254 Dose 30% Max Effect 40 mg (N=6), and PLACEBO (N=2). An unblinded interim analysis is conducted by the Study Team to confirm GO to Part 2 and refine Part 2 doses as needed. The timeline shows Day 1 Randomization, Follow-up at Day 10 for Part 1, and Day 1 Randomization, Follow-up at Day 7 for Part 2.
	
Design Features	
 This is a Phase 2a, global, multicentre, randomized, double-blind (Sponsor-unblinded), placebo-controlled, adaptive clinical trial to evaluate the antiviral effect, safety, tolerability and PK/ pharmacodynamics (PD) of GSK3640254 over 10 days in study Part 1 and over 7 days in study Part 2 in ART naïve HIV-1 infected adults, who are termed “participants” in the study. All participants will be screened for eligibility before being randomized, preferably within 14 days, into a 10-day treatment period in Part 1 and into a 7-day treatment in Part 2. The 14-day screening period may be extended to 28 days in some cases to allow receipt of all screening results and/or to accommodate scheduling.
Dosing	
 Part 1 will include approximately 14 randomized participants and will evaluate two active doses of GSK3640254, 200 mg once daily or 10 mg once daily, in cohorts of 6 participants each for 10 days. A cohort of 2 participants will be randomized to receive placebo for 10 days. Part 2 will include approximately 20 randomized participants and will evaluate three active doses of GSK3640254, 140/80/40 mg once daily, in cohorts of 6 participants each for 7 days. A cohort of 2 participants will be randomized to receive placebo for 7 days.
Time & Events	
 See Appendix 2: Schedule of Activities for additional details of activities
Treatment Assignment	
 All participants will be centrally randomized using an Interactive Voice/Web Response System (IVRS/IWRS).
Interim Analysis	
 An informal unblinded interim analysis of preliminary safety, tolerability, PK and antiviral activity occurred after participants of Part 1 completed their Day 12 visit.

2.4. Statistical Hypotheses / Statistical Analyses

Study 208132 is a proof of concept (POC), randomized double blind (Sponsor-unblinded) study to characterize antiviral activity, safety/tolerability, PK, and the relationship between PK and antiviral activity of GSK3640254 given once daily (QD), administered across a range of doses over 10 days in Part 1 and over 7 days in Part 2 in HIV-1 infected treatment naïve adults. No formal hypotheses will be tested.

3. PLANNED ANALYSES

3.1. Interim Analyses

An informal unblinded interim analysis of preliminary safety, tolerability, PK and antiviral activity occurred after participants of Part 1 complete their Day 12 visit. The analysis was accomplished following criterion defined in protocol Section 10.3.1.

Based on the results of the interim analysis, the dose levels for Part B were determined to be 140 mg, 80 mg, and 40 mg GSK3640254. Details of the Interim analysis displays are presented in [Appendix 11: List of Data Displays](#). The main statistical results are included in the ICPSR [GlaxoSmithKline Document Number [2019N405148_01](#). Study 208132].

3.2. Final Analyses

The final planned primary analyses will be performed after the completion of the following sequential steps:

1. All participants have completed the study as defined in the protocol.
2. All required database cleaning activities have been completed and final database release (DBR) and database freeze (DBF) has been declared by Data Management.
3. All criteria for unblinding the randomization codes have been met.
4. Randomization codes have been distributed according to RandAll NG procedures.

CONFIDENTIAL

208132

4. ANALYSIS POPULATIONS

Population	Definition / Criteria	Analyses Evaluated
Screened	
 All participants who were screened for eligibility 	
 Study Population
Enrolled	
 All participants who passed screening and entered the study. Note screening failures (who never passed screening even if rescreened) and participants screened but never enrolled into the study (Reserve, Not Used) are excluded from the Enrolled population as they did not enter the study. 	
 Study Population
Randomized	
 All participants who were randomly assigned to treatment in the study. This population will be based on the treatment the participant was randomized to. 	
 Study Population
Safety	
 All randomized participants who received at least one dose of study treatment. This population will be analysed based on the treatment the participant actually received. 	
 Study Population Safety
Intent-To-Treat Exposed (ITT)	
 All randomized participants who meet the study criteria and are enrolled into the study with documented evidence of having received at least one dose of treatment and at least one post-baseline HIV-1 RNA measurement. This will be the primary population for the final efficacy analysis for all active treatment groups. This population will be based on the treatment the participant was randomized to. 	
 Efficacy
Per-Protocol (PP)	
 all participants who meet study criteria and are enrolled into the study with documented evidence of having received all doses and all post-baseline HIV-1 RNA measurement. Protocol deviations that would exclude participants from the PP population are defined in Section 4.1 (Protocol Deviations) and Appendix 1: Protocol Deviation Management and Definitions for Per Protocol Population. The PP set will not be analysed if no participants drop out of ITT population. 	
 Efficacy
Pharmacokinetic (PK)	
 The PK Population will include all participants who receive GSK3640254 and undergo plasma PK sampling during the study. Participants for whom a plasma PK sample is obtained and assayed will be included in the listing of plasma GSK3640254 concentration-time data. Results from samples collected from a participant with emesis occurring within 2 hours of the dose will not be considered as evaluable. 	
 PK
Pharmacokinetic/ Pharmacodynamic (PK/PD)	
 Participants who meet criteria for Per-Protocol and Pharmacokinetic Population analysis sets and who undergo PD sampling during the study. 	
 Pharmacokinetic/ Pharmacodynamic

Refer to [Appendix 11](#): List of Data Displays which details the population used for each display.

4.1. Protocol Deviations

Important protocol deviations (including deviations related to study inclusion/exclusion criteria, conduct of the trial, patient management or patient assessment) will be summarised and listed.

Important deviations which result in exclusion from the analysis population will also be summarised and listed. (Please refer to [Appendix 1: Protocol Deviation Management and Definitions for Per Protocol Population](#)).

Protocol deviations will be tracked by the study team throughout the conduct of the study in accordance with the Protocol Deviation Management Plan (PDMP) [04 Nov 2019 Version 2].

- Data will be reviewed prior to unblinding and freezing the database to ensure all important deviations and deviations which may lead to exclusion from the analysis are captured and categorised on the protocol deviations dataset.
- This dataset will be the basis for the summaries and listings of protocol deviations.

A separate summary and listing of all inclusion/exclusion criteria deviations will also be provided. This summary will be based on data as recorded on the inclusion/exclusion page of the eCRF.

5. CONSIDERATIONS FOR DATA ANALYSES AND DATA HANDLING CONVENTIONS

5.1. Study Treatment & Sub-group Display Descriptors

Part 1 Treatment Group Descriptions			
RandAll NG		Data Displays for Reporting	
Code	Description	Description	Order in TLF
D1	GSK3640254 10 mg	GSK 10 mg	1
D2	GSK3640254 200 mg	GSK 200 mg	2
P	Placebo	Part 1 Placebo	3

Part 2 Treatment Group Descriptions			
RandAll NG		Data Displays for Reporting	
Code	Description	Description	Order in TLF
D3	GSK3640254 Dose 3	GSK 40 mg	4
D4	GSK3640254 Dose 4	GSK 80 mg	5
D5	GSK3640254 Dose 5	GSK 140 mg	6
P	Placebo	Part 2 Placebo	7

Data collected from protocol planned visits (ex. Lab, ECG, vital signs and PK etc.) will be analysed and reported separately for each part of the study, unless otherwise specified. Data collected from unplanned visits (ex. Adverse events, concomitant medications etc) or collected only once in study i.e. study population(ex. Demography , medical history etc.) will be reported two parts in single output. Unless otherwise indicated (in statistical models), randomized placebo participants from Parts 1 and 2 will always be treated as two groups for summaries tables. Besides, overall column will be added in all summary output.

5.2. Baseline Definitions

For all endpoints (except as noted in baseline definitions) the baseline value will be the latest pre-dose assessment with a non-missing value, including those from unscheduled visits. If time is not collected, Day 1 assessments are assumed to be taken prior to first dose and used as baseline.

CONFIDENTIAL

208132

Parameter	Study Assessments Considered as Baseline		Baseline Used in Data Display
	Screening	Day 1 (Pre-Dose)	
Efficacy			
All efficacy endpoints	X	X	Day 1
Safety			
All laboratory, vital signs and ECG measurement endpoints	X	X	Day 1

Unless otherwise stated, if baseline data is missing no derivation will be performed and baseline will be set to missing.

5.3. Multicentre Studies

Data will be summarised for all centres combined.

5.4. Other Considerations for Data Analyses and Data Handling Conventions

Other considerations for data analyses and data handling conventions are outlined in the appendices:

Section	Component
13.1	Appendix 1: Protocol Deviation Management and Definitions for Per Protocol Population
13.2	Appendix 2: Schedule of Activities
13.3	Appendix 3: Assessment Windows
13.4	Appendix 4: Study Phases and Treatment Emergent Adverse Events
13.4.1	Appendix 5: Data Display Standards & Handling Conventions
13.5.1	Appendix 6: Derived and Transformed Data
13.7	Appendix 7: Reporting Standards for Missing Data
13.8	Appendix 8: Values of Potential Clinical Importance
13.9	Appendix 9: Biomarker Analyses
13.10	Appendix 10: Abbreviations & Trade Marks
13.11	Appendix 11: List of Data Displays
13.12	Appendix 12: Example Mock Shells for Data Displays

6. STUDY POPULATION ANALYSES

6.1. Overview of Planned Study Population Analyses

The study population analyses will be based on the ITT population, unless otherwise specified. The study population analysis will include part 1 and part 2 together in one display (Part 1 placebo and Part 2 placebo displayed separately).

Study population analyses including analyses of participant's disposition, protocol deviations, demographic and baseline characteristics, prior and concomitant medications, medical history and exposure and treatment compliance will be based on GSK Core Data Standards. Details of the planned displays are presented in [Appendix 11: List of Data Displays](#).

6.2. Display Details

6.2.1. Subject Disposition

The disposition table will consist of all intent-to-treat participants

The number and percentage of participants who failed screening and were, therefore, not enrolled into the study, overall and by reason, will be summarized. A listing of the screen failure record for all participants who failed screening, including the reasons for screen failure will be presented.

Reasons for study treatment discontinuation will be summarized by treatment group and overall. A by-subject listing of reasons for study withdrawal, a by-subject listing of reasons for study treatment discontinuation, and a by-subject listing of planned and actual treatment received will be produced.

The number and percentage of participants at each visit will be summarized for each treatment group and overall.

6.2.2. Protocol Deviations

Please refer to Section [4.1](#) for details.

Inclusion and exclusion criteria deviations will be listed.

6.2.3. Populations analysed

The number of participants who were enrolled into the study, and the number of participants within each analysis population (screened, enrolled, randomized, ITT, Per Protocol, Safety, PK and PK/PD) will be summarized for each treatment group and overall.

The number and percentage of participants will be summarized by centre for each treatment group and overall.

Participants excluded from any population, including participants excluded from the Per Protocol population, will be listed.

6.2.4. Demography

The demographic and baseline characteristics age, sex, race, ethnicity, height, weight, BMI, and baseline CDC HIV-1 classification will be summarized by treatment group and overall for the safety population. The count, mean, standard deviation, median, minimum, and maximum value will be computed for age, BMI, height, and weight. A separate summary will be provided for age ranges.

A by-subject listing of demographic and baseline characteristics will also be produced.

Summaries of race and racial combinations will be produced for each treatment group and overall. A listing of race by subject will also be produced.

6.2.5. Medical Conditions and Medications

6.2.5.1. Medical Conditions

The number and percentage of participants with each past and current medical condition will be summarized for each treatment group and overall. Past conditions are those reported as ‘past’ and current conditions are those reported as ‘current’ at screening. Past and current conditions will be reported separately. Medical conditions will be summarised by category according to eCRF. By-subject listings of past and current medical conditions will also be produced.

A by-subject listing for HIV associated conditions will be produced.

6.2.5.2. Medications

For reporting purposes, medications will be classified as prior, concomitant using the associated start and stop dates recorded in the eCRF and relative to the first and last dose dates of investigational product (IP) (see [Appendix 4](#)). Medications will be coded using the GSK Drug coding dictionary (current version at the time of DBF).

Concomitant and prior medications will be summarised by GSK-Drug Anatomical Therapeutic Chemical (ATC) classification level 1 (body system) and ingredient. Drugs that are composed of a combination of ingredients will be displayed according to the ATC classifications of the ingredients, not of the combination.

The relationship between ATC level 1, ingredients and verbatim text for all medications in the study will be listed.

6.2.6. Exposure and Treatment Compliance

The complete dosing experience will be listed for all participants. The total duration of exposure (number of days on study drug), average daily dose, and cumulative dose will be summarized by treatment group.

CONFIDENTIAL

208132

For participants who completed the 10-day treatment period in Part 1 and 7-day treatment period in Part 2 of the study, the expected number of doses is 10 for Part 1 and 7 for Part 2. For participants who permanently discontinued the study treatment and/or withdrew from the study, the expected number of doses during the treatment period will be calculated using “Days on study drug” where “Days on study drug” is Last Dose Date – First Dose Date +1.

A summary of study medication compliance will be produced by treatment group: >0- <100%, 100%, >100%. The compliance will be calculated for the whole study treatment period as the percentage of cumulative dose [$100 * (\text{actual cumulative dose}) / (\text{expected cumulative dose for the participant's treatment duration})$].

For participants who completed the 10-day treatment period in Part 1 or 7-day treatment period in Part 2, the expected cumulative dose of GSK3640254 taken during the treatment period would be planned dose*10 days or planned dose*7 days. E.g. For participants who received 200 mg GSK3640254 in Part 1, the expected cumulative dose is 2,000 mg GSK3640254 (the 200 mg of IP is comprised of two 100 mg capsules of GSK3640254 administered daily over the 10-day treatment period).

For participants who permanently discontinued study treatment or withdrew early from the study, the expected cumulative dose of GSK3640254 taken during the treatment period would be the planned dose*(Last Dose Date – First Dose Date + 1).

The actual cumulative dose of GSK3640254 for all participants is the sum of all doses, in mg, of study drug consumed for the duration of the study. (Approach for handling missing treatment stopping dates is discussed in Section [13.7.2](#))

7. EFFICACY ANALYSES

Efficacy data will be listed and summarized according to GSK reporting standards, where applicable. Unless specified, efficacy tables will be reported separately for Part 1 and Part 2. Listings will be paginated by part, sorted by participant, day, and time, noting treatment; Descriptive statistics (n, mean, median, SD, min and max) will be calculated for continuous data and n and percentages will be calculated for categorical data.

Both the ITT and PP populations will be used for all efficacy analyses when there are participants excluded from the PP population. If there are no exclusions (i.e., if the PP and ITT population do not differ), then only the ITT population will be used for all efficacy analyses.

For summary tables, Plasma HIV-1 RNA values below lower limit of detection (LLOD = 50 copies/mL), will be imputed to 49 copies/mL. Otherwise, for listings, it will be listed as collected.

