6.1. Inclusion Criteria

Participants are eligible to be included in the study only if all of the following criteria apply:

Age

1. Participant must be 18 to 65 years of age inclusive, at the time of signing the informed consent.

Type of Participant and Disease Characteristics

2. Participants who are healthy (other than HIV infection) as determined by the Investigator or medically qualified designee based on a medical evaluation including medical history, laboratory tests, and cardiac monitoring.
3. Screening CD4+ T-cell count ≥ 350 cells/mm³
4. Documented HIV infection and Screening plasma HIV-1 RNA ≥ 5000 copies/mL. A single repeat of this test is allowed within a single Screening period to determine eligibility.
5. Treatment-naïve: No ARVs (in combination or monotherapy) received after the diagnosis of HIV-1 infection.

Weight

6. Body weight ≥ 50.0 kg (110 lbs.) for men and ≥ 45.0 kg (99 lbs) for women and body mass index (BMI) within the range 18.5-31.0 kg/m² (inclusive).

Sex

7. Male or female:

a. Female participants:

A female participant is eligible to participate if she is not pregnant (see [Appendix 5](#)), not breastfeeding, and not a woman of childbearing potential (WOCBP) as defined in [Appendix 5](#).

Informed Consent

8. Capable of giving signed informed consent, which includes compliance with the requirements and restrictions listed in the consent form and stated in the protocol.

Other

9. **For participants enrolled in France:** a participant will be eligible for inclusion in this study only if either affiliated to or a beneficiary of a social security category.
10. Participant must be willing and able to start cART on Study Day 8 (except in the case of early termination, clinically relevant AE/SAE, lab abnormality, the withdrawal of consent, lost to follow-up, etc., where circumstances could dictate otherwise).

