9.1. Efficacy Assessments

9.1.1. HIV-1 RNA Sampling

Plasma for quantitative HIV-1 RNA will be generated at timepoints listed in the SOA (Section 2).

An HIV-1 RNA PCR assay with a lower limit of detection (LLOD) of 40 copies/mL will be used.

Details concerning the handling, labeling and shipping of these samples will be supplied separately.

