10. STATISTICAL CONSIDERATIONS

10.1. Sample Size Determination

10.1.1. Sample Size Considerations

The primary objectives of this study are to investigate the safety, tolerability and antiviral activity of GSK3640254 over a 10-day treatment period in study Part 1 and over a 7-day treatment period in study Part 2. The antiviral activity will be assessed by estimating plasma HIV-1 RNA max change from baseline during the study.

The sample size for this study is based primarily on feasibility to provide adequate precision for the estimations.

Based on data from the short-term monotherapy study of BMS-955176/GSK3532795 POC (AI468002) study and GSK2838232 POC study, we assumed the maximum change from baseline viral load drop (VLD) values on log scale for individual participants from the higher dose in Part 1 follow a normal distribution. Therefore, we conducted 1000 trial

simulations in Fixed and Adaptive Clinical Trial Simulation (*FACTS*) software using the normal distribution with mean of change from baseline VLD on log scale at 0.5 to 2 copies, SD=0.4, and sample sizes=6 for Part 1 higher dose.

Using Bayesian calculation with non-informative priors for the mean and weakly informative priors for the error parameters, Normal (0, 100) for mean and Inverse Gamma (0.35, 0.0875) for error parameters, the posterior probability to achieve a clinically relevant cut-point of 1.3 log was calculated for each simulated trial, and percentage of the trials with posterior probability of mean viral load drop (VLD) at the higher dose in Part 1 >1.3 log (given the true mean VLD on log scale) $\geq 20\%$ was calculated and are shown below in [Table 5](#).

Table 5 Percentage of the trials with posterior probability $\geq 20\%$ for Part 1 higher dose using sample size=6

True Mean VLD on log scale	Posterior Probability $\geq 20\%$	Posterior Probability $< 20\%$
0.5	0.0%	100.0%
0.7	0.1%	99.9%
0.8	0.6%	99.4%
0.9	4.6%	95.4%
1	15.0%	85.0%
1.1	35.9%	64.1%
1.2	60.8%	39.2%
1.3	81.8%	18.2%
1.4	92.4%	7.6%
1.5	97.9%	2.1%
1.6	99.8%	0.2%
1.7	100.0%	0.0%
2	100.0%	0.0%

The precision of the dose response curve (with sample size N=6) is provided in [Table 1](#) (Section [5.5.1](#)).

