7.1. Primary Efficacy Analyses

7.1.1. Endpoint / Variables

- Change from baseline to the nadir (maximum change from baseline) in Plasma HIV-1 RNA
- Change from baseline to Visit 6 (Day 11 in Part 1 and Day 8 in Part 2) in Plasma HIV-1 RNA

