13.11.5. Efficacy Tables

Efficacy: Tables					
No.	Population	IDSL / Example Shell	Title	Programming Notes	Deliverable [Priority]
Plasma HIV-1 RNA (ITT)					
2.1.	ITT	EFF_T1	Summary of Plasma HIV-1 RNA – Part 1	On original and log10 scale	SAC
2.2.	ITT	EFF_T1	Summary of Plasma HIV-1 RNA – Part 2	On original and log10 scale	SAC
2.3.	ITT	EFF_T2	Summary of Change from Baseline to Nadir and Change from Baseline to Visit 6 (Day 11) in Plasma HIV-1 RNA – Part 1	On original and log10 scale	SAC
2.4.	ITT	EFF_T2	Summary of Change from Baseline to Nadir and Change from Baseline to Visit 6 (Day 8) in Plasma HIV-1 RNA – Part 2	On original and log10 scale	SAC
2.5.	ITT	EFF_T2	Summary of Time to Nadir in Plasma HIV-1 RNA – Part 1		SAC
2.6.	ITT	EFF_T2	Summary of Time to Nadir in Plasma HIV-1 RNA – Part 2		SAC
2.7.	ITT	EFF_T3	Summary of Modelled Plasma HIV-1 RNA Mean Rate of Change from baseline to Visit 6 (Day 11) and Maximum Change by Treatment – Part 1	On log10 scale	SAC
2.8.	ITT	EFF_T3	Summary of Modelled Plasma HIV-1 RNA Mean Rate of Change from baseline to Visit 6 (Day 8) and Maximum Change by Treatment – Part 2	On log10 scale	SAC
2.9.	ITT	EFF_T4	Summary of Proportion of Participants with Plasma HIV-1 RNA <400 and < 50 copies/mL – Part 1	By visit and by treatment	SAC

CONFIDENTIAL

208132

Efficacy: Tables					
No.	Population	IDSL / Example Shell	Title	Programming Notes	Deliverable [Priority]
2.10.	ITT	EFF_T4	Summary of Proportion of Participants with Plasma HIV-1 RNA <400 and < 50 copies/mL – Part 2	By visit and by treatment	SAC
2.11.	ITT	EFF_T5	Summary of Proportion of Participants with Plasma HIV-1 RNA Change from Baseline >1.5 log ₁₀ copies/mL Decrease -Part 1	By visit and by treatment	SAC
2.12.	ITT	EFF_T5	Summary of Proportion of Participants with Plasma HIV-1 RNA Change from Baseline >1.5 log ₁₀ copies/mL Decrease -Part 2	By visit and by treatment	SAC
Immunology (ITT)					
2.13.	ITT	EFF_T6	Summary of CD4+ and CD8+ and Change from Baseline by Visit – Part 1	Please include both absolute CD4 count and CD4 percentage, Same to CD8	SAC
2.14.	ITT	EFF_T6	Summary of CD4+ and CD8+ and Change from Baseline by Visit – Part 2	Please include both absolute CD4 count and CD4 percentage, same to CD8	SAC
2.15.	ITT	EFF_T3	Summary of Modelled CD4+ Cell Count Mean Rate of Change from baseline to Visit 6 (Day 11) by Treatment – Part 1	On log ₁₀ scale	SAC

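### The SAP uses an HIV-1 RNA detection limit of 50 copies/mL where the protocol's assay has 40; the primary-endpoint tables depend on it, so the two must be reconciled, though the effect is small

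*SAP*

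**What the plan says.** Protocol section 9.1.1: "An HIV-1 RNA PCR assay with a lower limit of detection (LLOD) of 40 copies/mL will be used".

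SAP section 7, for summary tables: "Plasma HIV-1 RNA values below lower limit of detection (LLOD = 50 copies/mL), will be imputed to 49 copies/mL". For the listings it adds: "Otherwise, for listings, it will be listed as collected".

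The primary endpoint in SAP section 7.1.1 is "Change from baseline to the nadir (maximum change from baseline) in Plasma HIV-1 RNA", alongside the change to Visit 6. Both are reported in summary tables. The Part 2 table (Table 2.4 in SAP section 13.11.5) is titled "Summary of Change from Baseline to Nadir and Change from Baseline to Visit 6 (Day 8) in Plasma HIV-1 RNA", and Table 2.3 is its Part 1 counterpart.

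SAP section 2.1 states that the analysis does not depart from the protocol. The figure 50 also appears in SAP section 7.2.1 as a secondary responder threshold, but section 7 does not refer to that threshold. It gives 50 as the detection limit itself.

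**The concern.** Two current texts give different detection limits for the same measurement, and the SAP gives no reason for its figure. The limit matters because it fixes the lowest viral load that can enter the tables. If the laboratory reports down to 40, a result of 40 to 48 is replaced by a higher number, and a result below 40 is set ten copies above the value that the same limit-minus-one rule would give at 40. The error runs one way: it makes the decline look smaller. It lies in the tables that report the primary endpoint.

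There is also a gap beside it. The imputation rule names summary tables only. The SAP does not say whether the mixed model (section 7.1.3.1) or the Emax fits (sections 10.1.4.1 and 11.1.3) use imputed or collected values, so the tables and the models could rest on different data.

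**Working it through.** **Inputs**

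- SAP limit 50, imputed value 49 (SAP section 7).
- Protocol limit 40 (protocol section 9.1.1). Limit-minus-one at 40 gives 39.
- Screening threshold (protocol section 6.1): "Documented HIV infection and Screening plasma HIV-1 RNA ≥ 5000 copies/mL".
- Planning values (protocol section 10.1.1): "mean of change from baseline VLD on log scale at 0.5 to 2 copies, SD=0.4, and sample sizes=6 for Part 1 higher dose".
- Priors (same section): "Normal (0, 100) for mean and Inverse Gamma (0.35, 0.0875) for error parameters".
- The distribution of baseline viral load is not in the documents. I assume 5000, 10,000 and 30,000 copies/mL as a range.

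**1. The plan's own figure.** No stated figure rests on the assay limit. The nearest is Table 5 of the protocol, which uses the maximum viral load drop: with n = 6 and a true mean of 1.3, 81.8% of trials reach a posterior probability of at least 20%. With the stated priors the posterior of the mean is a t distribution with 2(0.35) + 6 − 1 = 5.7 degrees of freedom and squared scale (2 × 0.0875 + SS)/(5.7 × 6), where SS is the sum of squares about the sample mean. Simulating 200,000 trials gives 81.3%; treating the SD as known at 0.4 gives 80.1%. Both are within 2 points. The known-SD version stays within 2 points on every row from 0.8 to 1.5. The t version is 2 to 3.5 points high at 0.9 to 1.1. The rows at 0.5 and 0.7 were not checked.

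**2. Error per participant**, if the limit is 40:

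- measured 40, analysed as 49: log10(49/40) = 0.088
- below 40, analysed as 49 instead of 39: log10(49/39) = 0.099
- 50 or above: zero

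From 5000 copies/mL, the largest recordable drop is log10(5000/49) = 2.009 with the SAP rule and log10(5000/39) = 2.108 with 39.

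**3. Who is affected.** The viral load must fall below 50. That needs a drop of more than log10(5000/50) = 2.00 from 5000, 2.30 from 10,000, or 2.78 from 30,000.

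**4. Effect on the group mean.** Individual drops are drawn from a normal distribution with SD 0.4, and every participant has the same baseline.

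| Baseline | True mean drop | Below 50 | 40 to <50 | Mean, floor 49 | Mean, floor 39 | Difference |
|---|---|---|---|---|---|---|
| 5000 | 1.3 | 4.1% | 1.7% | 1.295 | 1.298 | 0.003 |
| 5000 | 1.5 | 10.6% | 3.8% | 1.481 | 1.489 | 0.008 |
| 5000 | 2.0 | 50.0% | 9.6% | 1.845 | 1.889 | 0.044 |
| 10,000 | 1.3 | 0.6% | 0.3% | 1.299 | 1.299 | 0.0004 |
| 10,000 | 1.5 | 2.3% | 1.0% | 1.497 | 1.499 | 0.002 |
| 10,000 | 2.0 | 22.6% | 6.6% | 1.950 | 1.968 | 0.018 |
| 30,000 | 2.0 | 2.6% | 1.2% | 1.997 | 1.999 | 0.002 |

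Hand check of the third row: 50.0% − 9.6% = 40.4% fall below 40, and 0.404 × 0.099 = 0.040. The 9.6% between 40 and 50 add about 0.004. In that row most of the shortfall from 2.0 comes from the assay limit itself (2.000 − 1.889 = 0.111) and less from the SAP rule (0.044).

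**5. Other quantities.** At a true mean of 1.3 and a baseline of 5000, the share of trials passing the go criterion is 81.2% with floor 49 and 81.3% with floor 39. The proportions below 50 and below 400 do not change, since 49 and 39 are on the same side of both cut-offs. The response of more than 1.5 log10 could change only if baseline is about 49 × 10^1.5 ≈ 1550 copies/mL or less.

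**The case against.** The best case for leaving this alone is its size. The imputation is confined to summary tables, and the listings keep the collected values, so no data are lost. The group-mean shift is small beside a planning SD of 0.4. SAP sections 2.3 and 3.1 report the interim analysis as done and the Part 2 doses as chosen, so the go criterion is no longer open. SAP section 2.4 says that no hypothesis is formally tested. The documents give a limit of detection, not of quantification, so numeric results of 40 to 48 are an assumption. They also cannot show which limit the laboratory applied. All of this stands. It bears on size and on which document to correct, but does not remove the contradiction.

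Three stronger readings are tempting, and the documents do not support them.

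- A reader might infer that the imputed values distort the dose-response model. SAP section 7 limits the rule to summary tables, and section 10.1.4.1 describes the Emax response as the observed maximum change. What the models use is not stated, which is a gap and not a demonstrated error.
- A reader might infer that only the best responders are affected. The floor depends on the viral load reached. A drop of 2.05 log10 from 5000 ends near 45 and is affected; a drop of 3.0 from 100,000 ends at 100 and is not.
- A reader might infer that the final Part 2 visit, after cART starts on Day 8, makes the problem larger. Whether that visit belongs in the nadir is a separate question about the analysis window. Changing the floor would not settle it, and the documents do not show how many participants would be below 50 there.

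**Conclusion.** The mismatch between 40 and 50 is real, undeclared and unreconciled. It affects a stated rule for the primary-endpoint tables. If the assay limit is 40 and the laboratory reports numbers down to it, the decline is understated by at most 0.088 log10 for a measured value and 0.099 for a result below 40, and not at all for a participant who stays at 50 or above.

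The group-mean effect is 0.003 to 0.044 log10 with every baseline at 5000 and true mean drops of 1.3 to 2.0; at 30,000 it is at most 0.002. The 5000 case is an illustration at a low baseline and not a strict bound. The criterion applies at screening, whereas SAP section 5.2 takes the latest pre-dose value as baseline and sets no minimum. Whatever the baseline, the shift in a mean relative to a floor of 39 cannot exceed 0.099.

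This is a minor correction that should be made. It would be too strong to conclude that the primary endpoint is materially truncated or that its conclusion is in doubt.

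**What to change.** 1. Confirm the limit of the assay actually used, and make protocol section 9.1.1 and SAP section 7 agree.
2. If it is 40: analyse reported values of 40 to 49 as measured, impute 39 only for results reported as below 40, and keep 50 solely as the secondary responder threshold. The value 39 is a convention, but it follows the limit-minus-one pattern of the present rule and of the SAP's own rule for safety laboratory values reported as whole numbers (section 13.6.4).
3. If it is 50: correct protocol section 9.1.1 and leave the imputation as it is.
4. State whether the mixed model and the Emax fits use imputed or collected values.

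The cost is about one SAP sentence and one line of code for the limit, plus a sentence on the model inputs. No new data are needed, since the collected values are retained.
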